APPENDIX B

Preparation for Embolization with Irinotecan-Loaded HepaSphere Microspheres

As a general guideline, the loading of irinotecan into HepaSphere Microspheres will take 30 minutes. The HepaSphere Microspheres should not be used before they are fully hydrated and expanded.

1.0 Choose the appropriate dose of irinotecan solution to load into the HepaSphere Microspheres. A maximum dose of 100 mg irinotecan can be loaded in each vial of 25 mg HepaSphere MicroSpheres. Irinotecan solution is typically available in a concentration of 20 mg/ml.

2.0 Aspirate the irinotecan into a syringe connected to a needle of 20 gauge diameter or larger.

3.0 To ensure proper reconstitution of the HepaSphere Microspheres, grasp the HepaSphere Microspheres vial horizontally in your fingertips and roll the vial several times. This will transfer the dry contents of the vial to the sidewall.

Note: Pull back only the flip-top cap; do not remove the crimp ring or the stopper from the vial.

4.0 Carefully insert the needle of the syringe containing the irinotecan solution through the stopper of the vial. Continue rolling the vial in your fingertips and inject the irinotecan solution into the vial.

5.0 Place the HepaSphere Microspheres vial vertically. Carefully remove the syringe with the needle attached, and allow the vial to stand for 30 minutes in order to completely hydrate the spheres.

6.0 During those 30 minutes, shake the HepaSphere Microspheres vial several times back and forth so that the liquid contacts the grey stopper. Repeat this process every 2-3 minutes to ensure a homogenous reconstitution of the HepaSphere Microspheres.

Note: The vial is hermetically closed. Proper aspiration and/or venting techniques, as approved by the healthcare facility, may be used for easier injection of reconstitution media into the vial.

If aspiration of air from the vial is performed prior to reconstitution, exercise caution not to remove the spheres from the vial.

7.0 After the 30 minute hydration and loading period, attach a 20 gauge diameter or larger needle to an appropriately sized syringe and insert it into the HepaSphere Microspheres vial. Aspirate the contents of the HepaSphere Microspheres vial into the syringe. Rotate the vial to a vertical position with the bottom of the vial facing upward. Pull the needle back so that it is submerged in the liquid but not occluded by the stopper. Gently aspirate the entire contents of the vial into the syringe.

8.0 Prior to removing the needle from the HepaSphere Microspheres vial, while holding the syringe vertically, gently pull the plunger of the syringe down, removing any solution that may be in the hub of the needle.

9.0 Replace the needle with a syringe cap and invert the syringe back and forth to disperse the contents within the syringe.

10.0 Add an equal volume of non-ionic contrast medium to the syringe containing the irinotecan loaded HepaSphere Microspheres immediately before use.

11.0 Before any injection, check that the microspheres are in suspension. If not, invert the syringe back and forth to disperse contents within the syringe.

12.0 Do not remove the supernatant.

1. STUDY OBJECTIVES

1.1. PRIMARY OBJECTIVE

The primary study objective is the median overall survival of subjects treated with HepaSphere Microspheres loaded with irinotecan. Analysis will be performed when all subjects enrolled have been followed for survival for two years (24 months), are considered lost to follow up, or have died, whichever comes first. Survival time will be calculated in months and utilize the date of the first TACE procedure, the date of death (from any cause), and/or the last successful contact with the subject before they were considered lost to follow-up.

1.2. SECONDARY OBJECTIVES

Objective response rate (ORR), best tumor response, median liver progression-free survival, and time to progression will be analyzed based on mRECIST criteria as secondary objectives. Safety summaries will also be included.

1.3. EXPLORATORY OBJECTIVES

Other study objectives include analyzing pharmacokinetic (PK) blood samples, additional transarterial chemoembolization (TACE) cycles, RECIST 1.1 criteria, and clinical success.

2. BACKGROUND/INTRODUCTION

2.1. STUDY DESIGN

This prospective, single arm, post-market clinical trial is designed to demonstrate safety and efficacy of Merit Medical Systems' HepaSphere Microspheres loaded with irinotecan for subjects with metastatic colorectal cancer to the liver. There will be two hospitals participating in this study, one in Greece (N=100) and one in France (N=5). Hospitals and physicians with experience in routine use of chemoembolization for metastatic colorectal cancer (mCRC) to the liver will participate. Subject recruitment and offer to participate in the study will be at the investigator's discretion (ensuring that subjects are existing patients receiving care at the hospital and that they meet inclusion and exclusion criteria). All enrolled and treated subjects will be followed for survival until data analysis. Data analysis will be performed when all treated subjects actively being followed for survival have individually cumulated a minimum of two years (24 months) since the date of their first study TACE procedure.

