Median survival and time to progression were 21 months and 10 months among patients with less than 25% liver volume involvement, 7 months and 4.5 months among patients with 26-50% liver volume involvement, and 5 months and 3 months among patients with 51-75% liver volume involvement, respectively. According to RECIST criteria, 12 of the 25 surviving patients (48%) had stable disease; by EASL criteria, four patients showed complete response, four showed partial response, and four had stable disease. At 12 months of follow-up, one patient of the 12 with follow-up imaging (8%) had stable disease and the remaining 11 had progressive disease. Toxicities associated with the TACE procedures included upper abdominal pain (severe in 32% of patients, moderate in 40% and mild in 28%) and nausea (ECOG 3 in 12%, ECOG 2 in 43% and ECOG 1 in 45%).

Similar studies have been conducted with DC Bead®. Aliberti et al. performed an initial cohort study in 10 patients with liver-dominant mCRC refractory to systemic chemotherapy who underwent TACE with irinotecan-loaded DC Bead (Aliberti 2006). At one month of follow-up, all patients demonstrated significant reduction in tumor contrast enhancement and carcinoembryonic antigen (CEA) reduction of at least 50%. Objective tumor regression was observed in seven patients. The same research group published serial expansions of their cohort, eventually enrolling 82 patients (Fiorentini 2007, Aliberti 2011). Patients underwent one to four TACE cycles, and all showed reduction in metastatic contrast enhancement. At 3 months of follow-up 78% of patients demonstrated response by RECIST criteria, with a median duration of response of six months. Median survival across the entire cohort was 24 months, with 8 months of progression-free survival.

A later phase III study randomized 74 patients with less than 50% hepatic parenchymal replacement and no extrahepatic spread to TACE with irinotecan-loaded DC Bead and systemic fluorouracil, leucovorin and

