irinotecan (FOLFIRI) (Fiorentini 2012). At two years of follow-up, 56% of patients in the TACE group and 32% of those in the FOLFIRI group remained alive; survival dropped to 34% and 9% at 30 months, and 15% and 0% at 50 months among TACE and FOLFIRI patients, respectively. Progression-free survival was 7 months among TACE patients and 4 months among FOLFIRI patients ($p = 0.006$), but time to extrahepatic progression was not significantly different between the two groups. Objective response was observed in 68.6% of analyzed TACE patients and 20% of FOLFIRI patients. Severe neutropenia, diarrhea and mucositis were significantly more common among FOLFIRI patients, and liver enzyme and bilirubin elevations were significantly more common among TACE patients.

A U.S.-based cohort of 55 patients with liver-dominant mCRC who had received prior chemotherapy underwent TACE with irinotecan-loaded DC Beads and was followed for survival (Martin 2009). Adverse events were increasingly common with irinotecan dose escalation (50 mg to 200 mg). At 12 months of follow-up, 8 patients (15%) had complete response, 14 (25%) had partial response, 23 (42%) had stable disease and 10 (18%) had progressive disease according to mRECIST criteria (Martin 2011). Median overall survival for the cohort was 19 months, median progression-free survival was 11 months, and median hepatic-specific progression-free survival was 15 months.

Narayanan and colleagues have presented a retrospective analysis of 28 patients with hepatic metastases from CRC treated with irinotecan-loaded DC Bead (Narayanan 2013). These patients underwent one to five TACE procedures, and survived for a mean of 14.1 months. Complete response was observed in 3 (15%) patients, partial response was observed in 6 (30%), stable disease was observed in 4 (20%) and 7 patients (35%) showed progressive disease. The most common adverse events included nausea (47%), abdominal pain (43%), and vomiting (28%).

Only one publication to date has compared the efficacy of irinotecan-loaded HepaSphere Microspheres and DC Beads in the treatment of liver tumors (Namur 2015). In this study, performed in a VX2 rabbit model, treatment with irinotecan-loaded HepaSphere Microspheres resulted in significantly greater tumor necrosis and a significantly smaller area of residual tumor tissue than treatment with irinotecan-loaded DC Beads or bland HepaSphere Microspheres.

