2.1 Primary Objectives

- The primary study objective is the median overall survival of subjects treated with HepaSphere Microspheres loaded with irinotecan. Analysis will be performed when all subjects enrolled have been followed for survival for two years (24 months), are considered lost to follow up, or have died, whichever comes first. Survival time will be calculated in months and utilize the date of the first TACE procedure, the date of death (from any cause), and/or the last successful contact with the subject before they were considered lost to follow-up. Kaplan-Meier (product-limit) method will be used to assess median overall survival times.

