5.4 Survival follow-up

If a subject is no longer indicated for TACE, they will enter survival follow-up. During survival follow-up, subjects are contacted every three months (\pm 2 weeks) to determine their survival status. Subjects can be contacted (via phone, email, written response), their medical records reviewed, and/or information can be obtained from additional sources (i.e., the subject's caregivers/family members) to determine if the subject is alive. These survival contacts should continue until one of the following conditions is met:

- Subject dies
- Subject withdraws consent

- Subject is classified as lost to follow-up

Lost to follow-up (LTFU): All reasonable efforts will be made to obtain complete data for all subjects. Missing observations from unsuccessful contact attempts will occur due to some subjects being LTFU, having withdrawn from the study, or not adhering to required assessments. Three (3) total attempts shall be made to contact a subject. If a subject cannot be accounted for (i.e., by visit, telephone call, email, written response, family member report, etc.) and has not followed-up accordingly with the clinical site, they will be considered lost to follow-up. Study data collected on this subject, up to the date and time of loss to follow-up (or subject withdrawal) will remain in the study database and used for analysis purposes, as appropriate. These subjects will not be replaced. Survival follow-up information will be collected within the electronic database capture (EDC) system.

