APPENDIX A

Schedule of Procedures

	Screening ¹	TACE Procedure ²	Follow Up Visits ³	Survival Follow-up ⁴
Informed Consent	X			
Eligibility criteria assessment	X			
Demographics	X			
Medical History	X			
Tumor Evaluation / Imaging	X		X	
Hematology / Serum Chemistry	X			
Embolization procedures (TACE)		X		
Pharmacokinetic Sampling ⁵		X		
Additional cancer treatments			X	
Adverse Events		X	X	
Survival status				X

¹ Screening imaging must be within 4 weeks of first TACE cycle.

² First TACE cycle must be within 4 weeks of screening imaging. If the patient has bilobar disease, the embolization of the first lobe must be within 4 weeks of screening imaging and the second lobe must undergo embolization within 3 weeks (\pm 2 weeks) of the first lobe. A second TACE cycle is required for all patients 2-4 weeks after the first TACE cycle. Additional TACE cycles can be performed for residual or new disease as needed.

³ Follow up Visits will start 4-6 weeks after the second TACE cycle and occur every 12 weeks (\pm 2 weeks) thereafter during the first year of follow-up. Follow-up may be more frequent if medically indicated.

⁴ If patients are no longer indicated for TACE, they will continue to be followed for survival for 2 years after the first TACE procedure, with contacts performed every 3 months (\pm 2 weeks).

⁵ Blood samples will be drawn for PK analysis from a portion of study patients after the first TACE procedure at the following time points; 30 min, 1 hour, 4 hours, 12 hours, and 24 hours or prior to discharge (whichever comes first).

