5.2. PRIMARY DATA ANALYSES

Median overall survival times will be calculated using the Kaplan-Meier (product-limit) method and corresponding 95% confidence intervals will be generated. One- and two-year survival rates and corresponding 95% confidence intervals will also be calculated.

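### The documents disagree on when survival follow-up ends (2 years or data analysis); if the 2-year footnote is applied, the primary median overall survival or its upper confidence limit may not be estimable.

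*SAP*

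**What the plan says.** Three places govern the end of survival follow-up, and they differ.

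- **SAP 2.1 (Study Design):** "All enrolled and treated subjects will be followed for survival until data analysis". The analysis takes place once all treated patients still in follow-up have "individually cumulated a minimum of two years (24 months) since the date of their first study TACE procedure". Twenty-four months is therefore a floor, and early enrollees are followed for longer.
- **Protocol 5.4 (Survival follow-up):** "These survival contacts should continue until one of the following conditions is met". The conditions listed are death, withdrawal of consent and loss to follow-up. No time limit is given.
- **Schedule of procedures, footnote 4 (Protocol Appendix A, repeated in SAP 2.6):** for patients no longer indicated for TACE, "they will continue to be followed for survival for 2 years after the first TACE procedure".

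Protocol 2.1 and 7.1 and SAP 1.1 and 5.1 also mention two years, but only to time the analysis.

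On the estimator, SAP 5.2 states: "Median overall survival times will be calculated using the Kaplan-Meier (product-limit) method and corresponding 95% confidence intervals will be generated". One- and two-year survival rates with confidence intervals are planned as well. Protocol 2.1 and SAP 1.1 and 4.1 define survival time by death or by the last contact before loss to follow-up. They give no censoring date for a patient who is alive and still in follow-up at the analysis. Neither document says what is reported if the median is not reached.

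**The concern.** A Kaplan-Meier median exists only if the curve falls to 50% within the observed follow-up. Its upper confidence limit exists only if the upper confidence band also falls to 50%. A follow-up rule that stops at 24 months therefore matters when true median survival may lie near 24 months.

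The protocol's introduction gives reason to consider that case. Of the two studies cited for the sample size, the 82-patient cohort is reported with "Median survival across the entire cohort was 24 months". In the 74-patient randomized study, at two years "56% of patients in the TACE group and 32% of those in the FOLFIRI group remained alive".

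A site working from the schedule table could stop contacts at month 24, while one working from Protocol 5.4 would continue. At stake is whether the primary endpoint yields a point estimate with a two-sided interval.

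**Working it through.** The plan has no calculated sample size or event count to reproduce; the minimum of 100 was chosen by similarity to earlier studies. The counts agree: 100 + 5 = 105 (SAP 2.1) and 76 + 29 = 105 (SAP Table 7).

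**Inputs.** n = 105 (SAP 2.1 and Table 1). As a lower value, n = 83, the mRECIST denominator in SAP Table 5. The survival range comes from the protocol's introduction: a median of 19 months in the U.S. cohort, a median of 24 months in the 82-patient cohort, and 56% alive at 24 months in the randomized TACE arm. A 15-month median is added as an assumption.

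**Set-up for the footnote rule (assumed).** Every patient is followed to 24 months and censored there. The number alive, X, is then binomial(n, S), where S is true 2-year survival. Under exponential survival with median m, S = 2^(−24/m): 0.33 at 15 months, 0.417 at 19 and 0.50 at 24.

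**Median not reached.** This requires X/n > 0.5, so X ≥ 53 of 105 (X ≥ 42 of 83).

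**Upper 95% limit not reached.** This requires the upper bound of the curve at 24 months to exceed 0.5. The SAP does not name a transformation; log-log is assumed. With Ŝ = X/n, se = √[(1 − Ŝ)/(nŜ)] / |ln Ŝ| and U = Ŝ^exp(−1.96·se).

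- X = 42: Ŝ = 0.400, se = 0.130, U = 0.492, so the limit is reached.
- X = 43: Ŝ = 0.410, se = 0.131, U = 0.501, so it is not reached.

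The limit is therefore missing when X ≥ 43 of 105 (X ≥ 33 of 83).

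**Results (exact binomial tails).**

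| True 2-year survival | Median missing, n=105 | Upper limit missing, n=105 | Median missing, n=83 | Upper limit missing, n=83 |
|---|---|---|---|---|
| 33% (15-month median) | <0.001 | 0.05 | <0.001 | 0.12 |
| 35% | 0.001 | 0.12 | 0.003 | 0.21 |
| 40% | 0.02 | 0.46 | 0.03 | 0.56 |
| 41.7% (19-month median) | 0.04 | 0.60 | 0.06 | 0.68 |
| 45% | 0.15 | 0.82 | 0.18 | 0.86 |
| 50% (24-month median) | 0.50 | 0.97 | 0.50 | 0.98 |
| 56% | 0.89 | >0.99 | 0.86 | >0.99 |

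The randomized TACE arm is reported at 56% at 24 months and 34% at 30 months. Linear interpolation puts its median at 24 + 6 × (0.56 − 0.50)/(0.56 − 0.34) = 25.6 months; log-linear interpolation gives 25.4. Both lie just past a 24-month stop.

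**Same question under SAP 2.1.** Simulation used 1,500 runs per case, medians of 15 to 24 months or a curve through the randomized arm's reported rates, 0–20% loss over two years, and uniform accrual over 24 or 48 months. Accrual time and loss rates are assumptions. With follow-up to data analysis, the median is missing in at most 0.3% of runs in any case. The upper limit is missing in at most 12% with 24-month accrual and in under 1% with 48-month accrual.

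**The case against.** The strongest reply is that the plan already contains the better rule. Two body sections, SAP 2.1 and Protocol 5.4, set no 2-year stop. The outlier is a single table footnote, limited to patients no longer indicated for TACE, and it can be read as a minimum. This stands as far as it goes: every probability in the table is conditional on the footnote governing, and on its reaching all patients. But the footnote does not call itself a minimum, and it appears in both documents, so SAP 2.6 conflicts with SAP 2.1 within the same plan.

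A second reply is that the high-risk cases are optimistic for this trial. This also stands in part. The randomized study excluded extrahepatic spread, whereas this trial requires only that at least half the tumor burden be hepatic. If its 74 patients were split equally, the 56% carries an interval of 0.56 ± 1.96 × √(0.56 × 0.44/37), about 0.40 to 0.72. The one clinical series of this product reports medians of 21 months below 25% liver involvement and 7 months at 26–50%, and this trial admits up to 50%.

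Three stronger readings might be inferred, and the documents support none of them.

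- *The trial expects a median near 24 months.* The two studies are cited for size only and are not stated as survival assumptions.
- *The curve beyond 24 months will be biased because late deaths are captured while living patients are no longer contacted.* Neither document describes that practice, and it could not affect the curve before 24 months.
- *There is nothing to report if the median is missing.* One- and two-year rates with intervals are already planned, and a median reported as not reached is a valid Kaplan-Meier result.

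**Conclusion.** The contradiction is established from the text alone. Its consequence is conditional. If footnote 4 is applied to all 105 patients, loss of the median itself is unlikely at a true median of 19 months or less (0.04 or below) and an even chance at 24 months. At 56% two-year survival it is likely (0.89). Loss of the upper limit is the more common failure: about 0.05 at a 15-month median, 0.60 at 19 months and 0.97 at 24 months. The month-based figures assume exponential survival, and the upper-limit figures assume log-log limits. Under the rule in SAP 2.1, loss of the median is nearly eliminated and loss of the upper limit becomes uncommon.

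The documents do not support saying that the primary endpoint will fail, only that one of two conflicting rules exposes it to avoidable loss. Severity is moderate: the follow-up rule for the primary endpoint should be reconciled before the analysis.

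**What to change.** 1. Reword footnote 4 in Protocol Appendix A and SAP 2.6 to agree with SAP 2.1 and Protocol 5.4: survival contacts continue to one common data cut-off, with at least 24 months from first TACE for each living patient.
2. Name that cut-off in the SAP, and state in SAP 4.1 that patients alive at the cut-off are censored at their last contact on or before it.
3. Add one sentence to SAP 5.2: if the median or its upper limit is not reached, it is reported as such, alongside the one- and two-year rates already planned. Restricted mean survival to 24 months is an optional addition.

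The cost is two footnotes and a few SAP sentences, plus further 3-monthly contacts for early enrollees, which SAP 2.1 already implies. Protocol 5.4 allows survival status to be taken from medical records or family members, so some contacts not made after month 24 may be recoverable.

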2.2. TREATMENT GROUPS

The study is single arm and includes subjects with mCRC to the liver treated with HepaSphere Microspheres loaded with irinotecan.

2.3. STUDY POPULATION

Subjects (meeting inclusion/exclusion criteria and having signed informed consent) will be included in the study analysis if they have had at least one protocol specified TACE procedure.

2.3.1. Inclusion Criteria

The following inclusionary information must be evaluated by the investigator/institution to confirm the patient meets all the following criteria:

- Histologically or radiologically confirmed colorectal cancer metastases to the liver
- Patient is able to have either computed tomography (CT) or magnetic resonance imaging (MRI)
- Hepatic tumor burden $\geq 50\%$ of total tumor burden
- Hepatic tumor burden $\leq 50\%$ of total liver volume
- Not suitable for treatment by resection or percutaneous ablation at time of TACE treatment

- Life expectancy \geq 3 months
- World health organization (WHO) performance status \leq 2

2.3.2. Exclusion Criteria

The following exclusionary information must be evaluated by the investigator/institution to confirm the patient does NOT meet any of the criteria below:

- Previous treatment with any form of hepatic transarterial embolization
- Total bilirubin \geq 3.0 mg/dL
- Any contraindication for irinotecan administration
- Partial or complete thrombosis of the main portal vein
- Cardiovascular or respiratory failure
- Any other condition deemed exclusionary by the Investigator

